## I. Objectives

Menthol cigarettes contribute largely to the huge burden that smoking put on public health in the US. Nationally representative data show that ~43% of adults who smoke use menthol cigarettes with disproportionate trends among racial and gender minorities worsening persistent tobacco-related health disparities (e.g., 80% and 50% among Black and Hispanic adult smokers, respectively). Moreover, menthol cigarettes were shown to be “starter products” among youth, inducing more nicotine dependence, prolonging cigarette smoking, and making smoking cessation harder, especially at a younger age. The US Food and Drug Administration, lagging behind regulatory agencies in Canada and the European Union, recently proposed a rule to specifically ban menthol in cigarettes to reduce smoking prevalence and related health inequities. However, local US jurisdictions (states like California and Massachusetts and cities like San Francisco, CA and *Columbus, OH – effective Jan 2024*) have already enacted their own menthol ban. Yet the tobacco industry responded with lobbying, legal action (e.g., suing California State), and the introduction of synthetic cooling agents to cigarettes that could impart the same cooling effects as menthol. **Hence, assessing the impact of synthetic cooling agents on cigarette abuse liability is timely and critical.**

Synthetic cooling agents like Wilkinson Sword compounds (e.g., WS-3) may serve as an effective replacement to menthol. Like menthol, WS-3 elicits a cooling sensation by chemically activating the transient receptor potential melastatin-8 (TRPM8) in trigeminal nerves in the buccal cavity when inhaled and gives a deceptive cooling sensation. WS-3 could elicit the same impact as menthol in terms of smoothness-enhancing and bitterness-reducing of cigarette smoke leading to increased uptake among groups that are more sensitive to sensory impacts, like adolescents and young adults (AYAs). Indeed, synthetic cooling agents are currently widely used in electronic cigarettes (ECs), and these ECs are commonly used by AYAs. In addition, chemical analyses examining synthetic cooling additives in EC e-liquid have found that these cooling agents can be added at much higher concentrations than menthol without inducing harsh or aversive sensory effects. In response to the California menthol restriction, R.J. Reynolds introduced cigarettes with synthetic cooling agents that produce a cooling sensation without violating the menthol flavor restriction. These cooling agent non-menthol cigarettes are almost indistinguishable from their corresponding menthol cigarettes in terms of marketing and packaging. **There is a need to systematically assess if these new cooling agent cigarettes impart the same cooling perception among menthol smokers which will void any menthol restriction.**

Using a cross-over double-blinded study design, we will study the abuse liability (including sensory characteristics and appeal) of newly introduced cooling agent non-menthol cigarettes. Established young adult smokers will complete 3 clinic visits in which they smoke *ad-lib* one of three randomly assigned cigarettes that differ either by menthol or synthetic cooling agent content. The study cigarettes will include RJR brands Newport non-menthol box (control), Newport box (menthol), and Newport non-menthol mix box (cooling agent). Subjective effects and objective measures related to abuse liability and acute pulmonary effects (i.e., spirometry and nasal epithelial lining fluid [NELF]) will be evaluated. At each clinic visit, participants will also complete a forced choice task for a second ad-lib smoking session choosing between their usual brand cigarette or the study cigarette.

**Aim 1. Assess the content of synthetic cooling agents in newly introduced Newport cooling agent non-menthol, menthol, and traditional non-menthol cigarettes.** H1a: synthetic cooling agents will be present at high levels in cooling agent non-menthol cigarettes, H1b: synthetic cooling agents are present at low levels in other RJR cigarettes, and H1c: synthetic cooling agents are transferred intact to smoke, increasing the abuse liability of these new cigarettes, especially among young users.

**Aim 2. Assess the subjective effects and abuse liability of Newport cooling agent non-menthol cigarettes.** The cooling power of WS-3 is 150% that of menthol, hence, H1a: participants who smoke cigarettes with synthetic cooling agents will report greater cooling effects, more satisfaction, and greater demand in the

forced choice task, and H1b: puffing topography will be more intense (greater total puff volume) than the control and menthol conditions. H1c: Cigarettes with cooling agents (i.e., menthol or WS-3) will be more appealing than the control.

**Exploratory Aim 3. Examine acute changes to pulmonary health associated with Newport cooling agent cigarette use.** H3: Compared to menthol cigarettes, participants who smoke cigarettes with synthetic cooling agents will have decreased pulmonary functioning, increased markers of respiratory inflammatory and oxidative stress (e.g., IL-6, IL-8, 8-isoprostane, malondialdehyde), and decreased antiviral host-defense mediators (IFN $\gamma$ , IL6, and IL12p40), as measured via NELF samples.

## II. Background and Rationale

**Menthol, a cooling agent that increases nicotine dependence among smokers.** Menthol is a natural chemical compound extracted from peppermint and other plants in the *Mentha* genus. Due to its cooling effect, menthol is ubiquitously used in food, pharmaceuticals, cosmetics, toothpaste, and other consumer products. Menthol was first added to tobacco cigarettes in the 1920s and, currently, menthol cigarettes make up 37% of the US cigarette market. The cooling sensation that menthol exerts balances the aversive sensation of nicotine and tobacco smoke, leading to increased palatability which explains the widespread use of menthol in cigarettes by the tobacco industry. It is estimated that menthol cigarettes are responsible for 10.1 million new smokers, 3 million life years lost, and 378,000 premature deaths in the US from 1980 to 2018. The tobacco industry understood and capitalized on the impact of menthol on cigarette use, initiation among youth, and prolonged nicotine dependence. The industry manipulated menthol content in “starter products” to hook lifelong users at a younger age. The industry understood that menthol could act through different biological mechanisms to reinforce nicotine addiction, yet menthol’s chemosensory properties are the most important. Menthol elicits a cooling sensation as it chemically activates the transient receptor potential melastatin-8 (TRPM8). Menthol stimulates the TRPM8 in trigeminal nerves in the buccal cavity when inhaled and gives a deceptive cooling sensation. These sensory properties reinforce smoking and nicotine dependence among smokers, and are associated with higher nicotine intake from cigarettes. Puff volume, puff duration, and puffing frequency were reported to be significantly higher when smoking menthol cigarettes. This may explain the higher retention of toxicants when users smoked menthol cigarettes compared to matching non-menthol cigarettes. The impact of menthol on nicotine addiction is more pronounced among adolescents and young adults (AYAs), increases nicotine dependence, and makes it harder for them to quit smoking compared to non-menthol smokers, especially at a younger age. *The detrimental effect of menthol cigarettes on public health could be replicated in any tobacco product with cooling additives that evades tobacco regulation. In a recent example, following the California menthol restriction, R.J. Reynolds introduced cigarettes with synthetic cooling agents that produce a cooling sensation without violating the menthol flavor restriction.*

**The positive impact of menthol cigarette restrictions.** Longitudinal data from Canada showed that a nationwide menthol ban helped some menthol smokers quit smoking, yet the majority of pre-ban menthol smokers either switched to non-menthol cigarettes (59%) or managed to continue smoking menthol cigarettes (20%). Moreover, the ban did not significantly reduce smoking among adults or initiation among youth. These observations were also reported among EU menthol smokers after a similar ban. In the US, simulation and empirical studies have suggested that a federal menthol cigarette ban would benefit public health, but showed that a big proportion of menthol smokers may switch to other tobacco products, similar to observed trends in other nations. Also, data from the US and Canada showed that local menthol restrictions could help smokers quit and benefit public health. Hence, *local and federal menthol restrictions are beneficial to individual and public health. However, recently new synthetic cooling agents which have been added to cigarettes to impart the same cooling effects as menthol. These synthetic cooling agents do not impart a characterizing flavor of menthol, hence circumventing the menthol restriction. This study will provide much needed data to understand how these products may changes user behavior, the toxicant profile of these products, and data from this study will provide much needed scientific data to regulatory agencies regarding the*

*regulation of these new tobacco products.*

**Industry tactics to undermine menthol restrictions.** Historically, the tobacco industry responded to tobacco control measures by legal actions. These maneuvers were intended either to halt regulations that could help reduce tobacco use in the population (hence the industry profit) or at least delay the implementation of these regulations. Another tactic used by the industry was to modify tobacco products. For example, after the publishing of the Surgeon General report in 1964 that linked tobacco smoking to lung cancer and other diseases, the tobacco industry introduced light cigarettes and filtered cigarettes as “safer” alternatives to unfiltered regular cigarettes. In response to the menthol restriction in Canada and the EU, the tobacco industry introduced flavor accessories that could be used by customers to add menthol and other flavors to their cigarettes. The industry also introduced cigarettes with menthol-filled capsules in the filters to be crushed by the consumer during smoking. Another innovation, unique to the US to the best of our knowledge, was the introduction of synthetic cooling agents (i.e., WS-3) to cigarettes. These cigarettes are known as “cool non-menthol cigarettes.” *There is a need to assess the abuse liability and toxicity of synthetic cooling agents added to products labeled as non-menthol cigarettes and evaluate their potential to circumvent local and federal menthol restrictions.*

**Innovation.** This is the first study to systematically examine cool non-menthol cigarettes with synthetic cooling agents. As such, using novel methodologies developed by our study team, we will first determine the type and level of synthetic cooling agents added to these cigarettes. We will also examine how these additives differ from their menthol and non-menthol counterparts in terms of chemical profile and nicotine content. It is well established that positive sensory experiences are linked to continued and more frequent use of tobacco products. Because these new cigarette products recently emerged in the US marketplace, little is known about how these products may change appeal, use patterns, and the sensory experience. Thus, the findings which will support an R01 submission (Fall 2023), will provide the first data on how the addition of synthetic cooling agents changes the appeal and abuse liability potential of combustible cigarettes. Further, data on the inhalation safety of synthetic cooling agents are lacking. As such, we will be collecting the first assessment of how synthetic cooling agents added to cigarettes may alter the respiratory toxicity profile of combustible cigarettes. While this study incorporates the expertise of our research team, it also provides a foundational training opportunity for [name] (PI) to learn new techniques (i.e., forced-choice task, additive profile of tobacco products) while expanding her training in human laboratory research and the respiratory assessment of tobacco products.

### **Preliminary Studies.**

Given that these cool non-menthol cigarettes arrived on the US marketplace in January 2023, little is known about these products. However, data from a recently completed project provide some insight into how synthetic cooling agents alter e-cigarette (EC) use among young people. Drs. [name], [name], and [name], and [name] recently completed an observational clinical trial (2021 – 2022) among 85 young adult (aged 18 – 25) current EC users (daily or weekly use for at least 3 months). This study examined naturalistic differences in nicotine dependence, vaping preferences (flavor, device type), and puffing topography parameters [using participants' own device; total puff count, puff volume (mL), puff duration (sec), inter-puff interval (sec), puff velocity (mL/s), and total puff volume (mL)]. Most participants began vaping regularly at age 18 (71.8%; Mage = 18.5 years; SD = 2.2 years), had used ECs for about 3.6 years (61%; SD = 1.8 years), and reported moderate nicotine dependence (Hooked on Nicotine Checklist (HONC) total score, range 0 – 10, M = 5.3, SD = 3.4)). Most of the participants were using ECs preferred vaping ice variant products (60%, n = 51) which are flavors with synthetic cooling agents added (e.g., Blue Razz Ice, Lush Ice). Young adults who used ice flavors had greater puff duration (3.42 vs. 2.84 seconds for non-ice flavors). *These data highlight emerging evidence that the use of synthetic cooling agents is common in ECs, use is prevalent among young adults, and vaping synthetic cooling agent e-liquid is associated with increased puff duration.*

[figure not shown]
### III. Procedures

#### A. Research Design.

**Overview:** These pilot data are essential to supporting the R01 application as this is the first-time new cigarette products have emerged on the marketplace with synthetic cooling agents added. Evidence is needed to provide the FDA with guidance on how to regulate cigarette products with synthetic cooling agents and how this changes the abuse liability and appeal of these products as well as their potential to serve as a menthol replacement in the event of a menthol flavor restriction in the United States (and Ohio). Our team is uniquely suited to conduct both the behavioral and chemical analyses of these products.

**Proposed Study Design (Figure 1).** Prior to study enrollment, we will conduct chemical analyses for each study cigarette to determine the levels of additives including menthol and synthetic cooling agent levels (e.g., WS-3, WS-23). Using a cross-over double-blinded study design, we will study the abuse liability (including sensory characteristics and appeal) of newly introduced cool non-menthol cigarettes. Established young adult smokers (N=25; Ages 21 – 29) will complete 3 clinic visits in which they smoke *ad-lib* three matched cigarettes from the same brand that differ by menthol or synthetic cooling agent content. Participants will arrive at the session at least 12 hours nicotine abstinent. The study cigarettes will include Newport non-menthol box (control), Newport box (menthol), and Newport non-menthol mix box (WS-3). Subjective effects (e.g., cooling perceptions, appeal, satisfaction) and objective measures related to abuse liability (i.e., cigarette puffing topography, ) and pulmonary effects (i.e., spirometry and nasal epithelial lining fluid [NELF]) will be evaluated. Finally, participants will be presented with a second *ad-lib* smoking task (i.e., forced-choice task) where the participant will have the opportunity to choose between their usual brand cigarette and the study cigarette which will determine if the study product is preferred over their usual brand cigarette.

**Figure 1.** Study Design.

#### B. Sample

**Study Procedures. Chemical Analyses.** Tobacco samples will be extracted with isopropanol containing carvacrol as an internal standard. Nicotine, menthol, WS-3, WS-5, WS-12, and WS-23 will be quantified by GC-MS. The four synthetic cooling agents are selected based on information from the RJR website, or recently published data on other types of tobacco products. Briefly, ~1 g of tobacco will be extracted with 50 mL of the extraction solution. After shaking for 2 hours, a 1-μL aliquot will be analyzed by GC-MS using selected ion monitoring (SIM) and measurements will be conducted in triplicate (n = 3).

#### **Participant Screening and Enrollment:**

Phone and online screens will determine preliminary eligibility. Participants will complete an in-person screening prior to completing the informed consent. Following the informed consent, participants will complete a urine pregnancy test and twelve-hour nicotine abstinence (assessed via self-report, and eCO monitor) to confirm eligibility. If eligible, participants will then complete informed consent. Ineligible participants will be informed that they cannot participate and paid \$10 for their time. We will recruit 25 young adults (aged 21 – 29 years) established cigarette users (see inclusion criteria below, i.e., restricting our age range to young adults who can legally purchase these products). In our most recent studies recruiting young adult EC users (e.g., 20YVNR35490079; K01HL148907), we averaged 12 participant sessions per week and 80% retention (20% potential dropout rate). We will conduct analyses to examine attrition bias for those who complete the study and their non-complete counterparts. When able, we will collect data from participants who leave the study prior to completing (e.g., ask about time constraints, reasons for not returning, etc.). If we assume a similar recruitment rate, the proposed study can be completed in 3 months of data collection plus 9 months for clinical data analysis (3 months), NELF analysis (1 month), R01 submission (2 months), and data sharing/dissemination (3 months). Women, Children, Race/Ethnicity. We will recruit a sex-balanced sample. According to U.S. Census data, the racial composition of individuals living in Columbus is 53.9% Non-Hispanic White, 29% Non-Hispanic Black or African American, 5.9% Non-Hispanic Asian, 3.9% Hispanic White, and 3.7% Non-Hispanic multiracial. We expect that our distributions will be similar.

**Eligibility Requirements.** Inclusion criteria: (1) aged 21 – 29 years; (2) established cigarette user (at least 100 lifetime cigarettes and currently use ≥5 cigarettes/day or weekly use over the past 3 months); (3) willing to provide informed consent and abstain from using tobacco products 12 hours prior to the three lab sessions; and (4) read and speak English. Exclusion criteria: 1) recently COVID-19+ (defined as a positive test in the past 30 days) or a recent COVID-19 hospitalization (within the past 6 months); 2) self-reported unstable or significant psychiatric conditions (past and stable conditions will be allowed; this will be confirmed via self-report); 3) history of cardiac event or distress within the past 3 months; 4) are currently pregnant, planning to become pregnant, or breastfeeding (will be verified with urine pregnancy test); 5) currently attempting to quit using combustible tobacco products; and (6) have suffered from any serious lung disease or infection (e.g., tuberculosis, cystic fibrosis, or lung cancer) in the past 30 days.

**Recruitment Feasibility and Retention.** We will recruit our sample from a combination of resources, including the CTR databases of past participants (N = 1952; n = 1377 within our age range). The only demographic variables collected on the screener are age, gender, and sex assigned at birth. For gender 351 (26%) identify as male, 985 (72%) identify as female, and 40 (3%) are another non-binary gender.). Participants will primarily be recruited for this study through flyers/social media. Our recruitment language will contain a brief overview of our study, a link to an online screener, as well as contact information (email, phone) for our lab. Young adults who are interested in participating can fill out the screener online through the link or over the phone. In the screener, we will ask individuals to provide us with their preferred form of contact (home phone, cell phone, email). We will make it

clear in the screener that providing this information gives us permission to contact the individual about further participation in the study if eligible.

**Retention:** Participants who drive will be provided with free parking, \$80 for each visit that they attend (\$240 total), and an additional bonus of \$50 for protocol compliance (attending all 3 visits) for a possible total of \$290. To be more inclusive and equitable to participations who do not have access to reliable transportation, we are also budgeting up to \$25/visit to use Lyft/Uber rideshare services. We will also facilitate retention by: 1) obtaining multiple sources of contact; 2) offering weekend appointments, and 3) reminder calls/texts/emails.

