### C. Measurement / Instrumentation

To facilitate adherence to the 12-hour nicotine abstinence (verified via exhaled carbon monoxide [abstinence range = 3–4 ppm]), efforts will be made to complete all study visits in the morning hours (~7:00 AM–11:00 AM), near the participant's typical waking time. Randomization to condition order will be completed prior to study Visit 1. To ensure eligibility, pregnancy exclusion will be confirmed with a urine test (pregnancy tests will be completed at each visit throughout the study). Questionnaires will provide basic demographic and tobacco use history information. Participants will complete the pre-smoking respiratory assessments (spirometry and NELF collection). Spirometry will be completed in the standing position. Nasal Epithelial Lining Fluid (NELF) samples will be collected as described before. Briefly, the absorbent matrix cut to fit within the nasal passages will be inserted into the inferior nasal turbinate, and the matrix will be clamped in place with a padded nose clamp for 2 min after which the strips will be removed and placed into microfuge tubes and frozen. Samples will be extracted for assessment of inflammatory mediators (cytokines and chemokines; e.g., IL-6, IL-8), mediators of host defense status (IP-10, IL-1 $\beta$ , IFN $\gamma$ ) via multi-plex (Mesoscale Diagnostics). Then, participants will move to our negative pressure room to complete the first smoking session. Puffing Topography will be measured with a validated cigarette puff topography device (eTOP®) that records puff count, puff duration, inter-puff interval, puff flow rate, puff volume, and total puff volume. Participants will be instructed to smoke the study cigarette. Then, questionnaires (i.e., pre/post smoking) will capture specific behavioral and subjective effects associated with abuse liability, specifically as it relates to cooling perception (Table 1). Appeal and Sensory Quality will require participants to rate each product on visual analog scales (range, 0-100; liking and willingness to use again) and sensory characteristics (e.g., olfactory response, somatosensory responses, flavor intensity (very intense – no intensity), sensation intensity (very intense – no intensity), pleasantness of taste + sensation (very pleasant – very unpleasant, cooling power/intensity). The Drug Effects Questionnaire (DEQ) will be used to rate acute responses to the cigarette on visual analog scales (range, 0 “not at all” – 100 “extremely”). Items assess liking/wanting (the average of “I feel good cigarette effects,” “I want more of that cigarette I received,” “I feel the cigarette strength,” and “I like the cigarette effect”). Modified Cigarette Evaluation Questionnaire (mCEQ) will be used to measure domains of reinforcement (vaping satisfaction, psychological rewards, and aversion; e.g., “Was the product satisfying?” on a 7-point scale (e.g., 1 “not at all”, 4 “moderately”, 7 “extremely”). Nicotine withdrawal will be assessed using the empirically validated 15-item version of the Minnesota Nicotine Withdrawal Scale (MNWS). The Cigarette Purchase Task will assess economic demand (puffs) via questionnaire. During this questionnaire, participants will be asked to indicate the quantity of puffs they would hypothetically purchase and use if it was available at incrementally increasing prices ranging from \$0 (free) to \$100. Participants will be instructed to assume they were purchasing cigarette puffs for their consumption in 24 hours. Finally, participants will be presented with a second ad-lib smoking task (i.e., forced-choice task) where the participant will have the opportunity to choose between their usual brand cigarette and the study cigarette which will determine if the study product

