**Study Visit 1:** To ensure eligibility pregnancy exclusion will be confirmed with a urine test (pregnancy tests will be completed at each visit throughout the study). We will also ask participants to provide an exhaled breath sample to determine adherence to 12-hour nicotine abstinence (exhaled carbon monoxide [eCO]).

Informed consent will be obtained, and participants will provide basic demographic and product use history information. At the start of each visit, we will assess participants' height, weight, and blood pressure. Next, participants will complete computer-based spirometry testing and airwave oscillometry, which will measure central obstruction, peripheral obstruction, and dynamic collapse. Participants will also provide the first of two NELF samples. Then, participants will move to our negative pressure vaping room to complete the first smoking session and will be randomized to use the first product of the three conditions (i.e., non-menthol control; menthol; synthetic cooling agent). The study RA will connect the study to the topography device. Puff Topography will be measured with a validated puff topography device. The device uses a pressure transducer integrated into a plastic holder to produce measures of puff count, puff duration, inter-puff-interval, puff flow rate, average puff volume, and total puff volume. Participants will be instructed to smoke ad libitum. Next, participants will repeat the respiratory assessment, provide the final NELF sample, and complete questionnaires (see table 1) to capture specific domains (i.e., perceived effects, behavioral) associated with abuse liability. Lastly, participants will return to the negative pressure rooms to participant in the final smoking session. Participants will complete a forced choice task, in which they will choose if they would prefer to smoke their usual brand cigarette, or the study cigarette provided to them during this

session.

**Study Visits 2 - 3:** All procedures will be followed as outlined above in study session 1.

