There are minimal risks associated with this protocol. The protocol requires young adult (aged 21 – 29 years) current tobacco users to undergo 12 hours of nicotine abstinence on three occasions and to smoke three different types of commercially available cigarettes. The risk of side effects and adverse events are very low. These products are available at a variety of stores nationwide, without a prescription. Nevertheless, all participants will be screened for general medical precautions (e.g., pregnancy, cardiovascular disease) and monitored for adverse events during the study period. Study personnel will assess for adverse events via self-report at all visits. Any serious adverse events will be reported following guidelines outlined in the Data Safety and Monitoring Plan. We will withdraw participants who have a serious adverse event or become pregnant or begin to breastfeed. Identifying information will never be reported in any publication. Nicotine abstinence can lead to withdrawal symptoms that include irritability, anxiety, restlessness, hunger, and difficulty sleeping. The effects can be uncomfortable but are not dangerous. The risk of undermining cessation is also potential risk; however, we will only recruit users not currently engaged in a cessation attempt, and we will provide all participants at the end of the study with a referral for cessation services (e.g., Quit Line).

Protection against loss of confidentiality and privacy will be maintained by numerically coding all data, disguising identifying information, and keeping data locked in file drawers or in a secure, password-protected database. Only study research assistants and the PI will have the information that connects participant's name and ID number. All electronic data will be numerically coded and stored in a password protected database, on a password protected computer in a secure research space. Participant information will be accessible only to research staff, who are pledged to confidentiality and complete training in the ethical conduct of research (i.e., both HIPAA and CITI trainings). Identifying information will not be reported in any publication.

Whereas no assurance can be made to an individual participant that s/he will personally benefit from this research, the experience should be beneficial. The immediate benefits of this research are

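### Colds and nasal allergy are not checked at each visit or linked to the NELF and spirometry analysis, which can add avoidable noise to Exploratory Aim 3

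*Combined protocol and SAP*

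**What the plan says.** **Outcomes.** Exploratory Aim 3 (I. Objectives) predicts higher inflammatory markers and "decreased antiviral host-defense mediators" in nasal epithelial lining fluid (NELF), together with poorer lung function. Section III.C describes part of the same panel as "mediators of host defense status".

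**Entry criteria (III.B, Eligibility Requirements).** Two exclusions concern the airways. One is COVID-19: a positive test within 30 days or a hospitalization within six months. The other is to "have suffered from any serious lung disease or infection (e.g., tuberculosis, cystic fibrosis, or lung cancer) in the past 30 days". Common cold, sinusitis, allergic rhinitis and nasal sprays are not named.

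**Visit procedures (III.C, Table 1, III.D).** The repeated items are:
- a pregnancy test ("pregnancy tests will be completed at each visit throughout the study");
- exhaled CO;
- basic measurements ("At the start of each visit, we will assess participants' height, weight, and blood pressure");
- spirometry and oscillometry;
- NELF before and after the first smoking session;
- the questionnaires.

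For Visits 2 and 3 the plan says only "All procedures will be followed as outlined above in study session 1". The nearest health query is under Protection Against Risk: "Study personnel will assess for adverse events via self-report at all visits".

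**Analysis (III.F).** Aim 3 uses a linear mixed model per outcome to compare cigarettes. There is no illness covariate and no sensitivity analysis for illness. The section does not say whether the condition contrast is on the post-smoking level, the within-visit change, or the post-smoking level adjusted for the pre-smoking value.

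**The concern.** A participant with a head cold or active nasal allergy at Visit 2 is sampled like anyone else. Nasal illness can plausibly move inflammatory and host-defense mediators at the very site sampled, for reasons unrelated to the cigarette. The plan accepts this in principle when it excludes recent COVID-19, but it repeats no such check later and leaves other upper-airway illness unaddressed.

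With three visits per person and roughly 20 completers, a few such visits could widen the NELF contrasts or fall unevenly across cigarettes. Spirometry is exposed in the same way. Symptoms not recorded on the day cannot be reliably recovered later, so even a sensitivity analysis would be closed off. The data are meant to support a larger grant application.

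**Working it through.** **The plan's own figure.** Section III.F states 60-40% power for large differences with 25 subjects. It gives no effect size, SD or correlation and is not specific to NELF. It cannot be reproduced from its own inputs and is not used here.

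**Inputs from the plan.** N = 25; three visits each; 80% retention, so 25 × 0.8 = 20 completers; two-sided alpha 0.05; 12 sessions per week.

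**Assumed inputs (not in the documents).** The share of visits affected, p, is 3%, 5% or 10%. Mediator SD is 0.2 log10 per visit, the true cigarette difference is 0.15 log10, and an affected visit is shifted by S = 0.5 to 1.0 log10. A fraction r of that shift survives in the analysed outcome: r = 1 if post-smoking levels are compared, r < 1 if within-visit change is used. The same SD is assumed in both cases. The test is one unadjusted paired t-test, standing in for a contrast from the mixed model.

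**Step 1: how many visits.** Expected number = visits × p. The chance of at least one is 1 − (1 − p)^visits.
- All 25 participants, 75 visits: 75 × 0.03 = 2.25; 75 × 0.05 = 3.75; 75 × 0.10 = 7.5.
- 20 completers, 60 visits: 1.8, 3 and 6 expected; chance of at least one 84%, 95% and over 99%.
- Chance that two cigarettes differ by three or more affected participants (n = 20): 7% at p = 5%, 18% at p = 10%.

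**Step 2: no illness.** SD of the paired difference = √(2 × 0.2²) = 0.283. Standardized difference = 0.15 / 0.283 = 0.53. Power with n = 20 is 0.61.

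**Step 3: with illness.** SD of the paired difference = √[0.08 + 2p(1 − p)(rS)²]. For p = 5%, r = 1: √(0.08 + 0.095 × 0.25) = 0.32 at S = 0.5, and √(0.08 + 0.095) = 0.42 at S = 1.0. Power is simulated, because the mixture is not normal. Ranges run from S = 0.5 to S = 1.0.

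| Outcome analysed | SD, 5% of visits | Power, 5% | SD, 10% of visits | Power, 10% |
|---|---|---|---|---|
| Post-smoking level (r = 1) | 0.32-0.42 | 0.51-0.37 | 0.35-0.51 | 0.44-0.26 |
| Change, half the shift left (r = 0.5) | 0.29-0.32 | 0.58-0.51 | 0.30-0.35 | 0.56-0.44 |
| Change, a quarter left (r = 0.25) | 0.29-0.29 | 0.60-0.58 | 0.29-0.30 | 0.60-0.56 |

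Simulation runs differ by about 0.01. If the shift cancels completely between the two samples, there is no loss.

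**Step 4: bias and type I error.** With order randomized, illness is equally likely under each cigarette. The mean spurious difference is about zero, and type I error stayed at about 5% in every scenario.

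**Step 5: a second parameterization.** Take a standardized difference of 0.6, n = 20, 10% of visits affected, and shifts of 1, 2 or 3 SDs of the paired difference. Power falls from 72% to 65%, 50% or 37% for post-smoking levels, and to 71%, 70% or 68% if a quarter of the shift remains. The pattern is the same.

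**The case against.** **A health query exists.** A reader might infer that pregnancy and exhaled CO are the only checks repeated at each visit. They are not: blood pressure, height and weight are taken, and adverse events are asked about every time. The reporting rules also cover worsening of an intermittent pre-existing illness, so a cold or an allergy flare could be captured. This stands. The gap is that nothing connects such a record to NELF, spirometry, rescheduling or the model.

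**The design samples before and after smoking.** Table 1 and III.D say so, and Aim 3 speaks of acute changes. An illness present all morning raises both samples, so the large losses in the first row of the table may never arise. This stands as far as the design goes, but III.F does not commit the condition contrast to a change or baseline-adjusted form. Nor would such a form remove an illness-related alteration of the response to smoking.

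**The inputs are assumed.** This stands too. The assumed shift is 2.5 to 5 times the assumed per-visit SD, and the documents give no illness rate. A reader might also infer that the markers were selected because they respond to infection; the plan presents them only as markers of inflammation and host defense.

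**The aim is exploratory.** The study is a pilot that calls itself underpowered, and the NELF problem does not touch Aims 1 and 2.

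**A screen may sit elsewhere.** Section III.E promises standard operating procedures, which could include a day-of-visit check. That cannot be confirmed from the plan.

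**Conclusion.** The omission is real and its consequence is modest. The plan would sample symptomatic visits and has no dedicated record or rule for handling them. The cost is added variance and chance imbalance. A reader might go further and conclude that the NELF results would be driven by who had a cold, or that illness would favour one cigarette. Randomized order and blinding do not support that: the expected bias is zero and type I error is not inflated. A false positive produced by illness is part of the ordinary 5%.

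The size depends mainly on an unstated analysis choice. With 5-10% of visits affected and the assumptions above, power falls from 0.61 to somewhere between 0.51 and 0.26 for post-smoking levels. It falls only to about 0.60 to 0.56 for within-visit change with a quarter of the shift remaining. Severity is minor and confined to Exploratory Aim 3 (NELF and spirometry).

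**What to change.** 1. At the start of every visit, before NELF, record a short fixed set of items in REDCap: cold, flu or COVID symptoms or a positive test; active nasal allergy; nasal spray use.
2. Reschedule symptomatic visits where feasible, under a rule that the investigators write in advance.
3. State in III.F that post-smoking NELF and spirometry are analysed with adjustment for the same-visit pre-smoking value.
4. Keep all visits in the main Aim 3 model, and prespecify a sensitivity analysis without symptomatic visits. Dropping them from the main model would discard data from a sample of about 20 and is harder to defend.

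**Cost.** A few minutes per visit and a handful of delayed visits. Capacity looks sufficient: 75 sessions at 12 per week take 75 / 12 = 6.25 weeks, against about 13 weeks in the projected three months of data collection. That projection is a feasibility estimate and not a visit window, so it shows only that there is room to move visits.
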